Additionally, exercise training in MetS patients was also associated with a significant reduction in high-sensitivity C reactive protein, and insulin resistance, but independent of weight loss [10], being this last effect (i.e., weight loss) a non-necessary aim into morbid obese patients. However, considering that the cardiorespiratory fitness (CRF) have been reported to be a strong predictor of overall health, exercise training may improve CRF in patients with MetS [11, 12], and thus we speculate that the CRF related outcomes such as the walking perform can be relevant for the health in obese patients at risk of MetS. Additionally, the resistance exercise training (RT, i.e., a particular exercise training modality consisting in stimulating muscles using external weights), may help to reduce health markers as systolic blood pressure (SBP) in obese patients with MetS risk factors [13]. In addition, supervised RT improved muscle strength and functional capacity in patients with obesity undergoing bariatric surgery [14]. However, although RT has been widely studied in obesity [15], there is little information in the morbid obesity. On the other hand, there is poor knowledge similarly, about the interindividual variability to exercise training in terms of responders and non-responders (NR). For example, as in reducing fat markers, we have shown that more baseline fat (overweight, obesity) have showed higher fat decreases and thus less NR, we speculate that morbid obese patients could decrease more both fat and MetS markers than other peers with less fat as those with obesity. Objectives: to determine the effects of a resistance training programme (RT) in preventing or attenuating metabolic syndrome (MetS) in patients with morbid obesity. A second aim was to report the prevalence of NR in terms of improvements in MetS markers and other co-variables considered. Design: An experimental, and non-randomized control clinical study. Methods: In an experimental clinical trial, obese and morbid obese patients will be invited for participating in a lifestyle study including resistant training during 20 weeks for preventing MetS in this cohort. Participants will be

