

Statistical Analysis Plan (SAP): We will apply 2 main forms of statistical analyses a) to report the pre-post changes in mean terms, and b) to report the results according with the inter-individual responses based on the technical error criteria, where according with the error calculated in the three previous measurements registered by the sample that was voluntary. Thus, for example, we will classify the subjects in responders and non-responders by the technical error of measurement, and additionally, we will classify the subjects according with a responder and non-responder clinical criteria, where we will classify as responders to all subjects who can be able of changing an initial adverse clinical altered profile for a healthy new classification. Thus, the specific statistical methods that we hope to apply for each analysis are; test of normality and homoscedasticity assumptions using Shapiro-Wilk and Levene's tests, the Student's t test for the identification of differences at baseline. An ANCOVA will be conducted (for potential confounders outcomes) in those altered baseline differences outcomes. We also hope to apply the repeated measures of two-way (group, time) to assess occurrence of an actual training effect [i.e., $p < 0.05$ for the interaction (group \times time) for the different study outcomes]. Among the specific statistical methods we hope to apply the Bonferroni post hoc test we hope to apply when we can be seen test differences among groups. Similarly, we hope to apply the Cohen's d test in order to detect effect size, using the threshold values of 0.20, 0.60, 1.2, and 2.0 for small, moderate, large, and very large effects, respectively [18], with 95% confidence intervals (CI). The alpha level was fixed at $P < 0.05$ for statistical significance.

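### A training effect is declared outcome by outcome at p<0.05, with no primary outcome named, no error control across outcomes and no syndrome-level analysis of MetS, the main objective

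*Combined protocol and SAP*

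**What the plan says.** The Objectives give the main aim as "to determine the effects of a resistance training programme (RT) in preventing or attenuating metabolic syndrome (MetS) in patients with morbid obesity". The second aim is "to report the prevalence of NR in terms of improvements in MetS markers and other co-variables considered". The Design line reads "An experimental, and non-randomized control clinical study".

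The SAP plans a two-way (group, time) repeated-measures analysis "to assess occurrence of an actual training effect". The criterion is an interaction p-value below 0.05, applied "for the different study outcomes". Alpha is fixed at 0.05, with no overall or family-wise level given.

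Three other SAP statements bear on the point:

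- **Multiplicity:** "the Bonferroni post hoc test we hope to apply when we can be seen test differences among groups".
- **Baseline adjustment:** "An ANCOVA will be conducted (for potential confounders outcomes) in those altered baseline differences outcomes".
- **Clinical response:** responders are participants capable of "changing an initial adverse clinical altered profile for a healthy new classification".

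The documents contain no list of outcomes and designate none as primary. The sample-size text rests on feasibility and a pilot study and names no outcome either. The SAP does not mention MetS. A published harmonised definition is cited in the Scientific background but is not adopted for analysis.

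**The concern.** The plan states a decision rule for each outcome but does not connect it to the question the trial asks. MetS is described in the background as a cluster of five factors. A mixture of significant and non-significant markers is a quite possible result, and the plan has no rule for saying whether such a mixture means MetS was attenuated. The choice of which marker answers the objective would then be made after the results are known.

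Two further gaps make this worse. The SAP does not say what the group factor is. The Design line implies a control group, but the background also speculates that patients with morbid obesity will improve more than less obese peers, and entry covers BMI classes II and III. In addition, ANCOVA is used only for outcomes that differ at baseline, so the form of the analysis for any given outcome depends on a preliminary test.

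**Working it through.** **No figure to reproduce.** The documents give no sample size, power or overall alpha. The only error rate is 0.05 per test, which is an input.

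**Does anything in the SAP serve as a test of MetS?**

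- *The interaction test.* It is a between-group test and would presumably cover individual MetS markers. It is applied marker by marker, and no step combines the markers into status, a count of criteria or a severity score.
- *Bonferroni.* It compares groups within an outcome. It leaves the error rate across outcomes unchanged.
- *The clinical-responder rule.* It does not name MetS, does not say whether it works per marker or for the syndrome, and has no stated between-group test. It counts only people who start with an adverse profile, so it cannot show prevention in those without MetS at baseline.

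**Size of the multiplicity problem (illustration).** Inputs:

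- m = 5, the components listed in the Scientific background: abdominal obesity, hypertension, triglycerides, HDL and hyperglycaemia.
- 0.05 per test, from the SAP; two-sided testing is assumed.
- Equal correlation between test statistics of 0, 0.5 or 0.7 (assumed).
- No true effect on any component, and any one significant result read as a MetS effect (assumed; the plan does not say so).

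For independent tests, P(at least one false effect) = 1 − (1 − 0.05)^5 = 1 − 0.95^5 = 0.226.

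For equal correlation ρ and cut-off c = 1.96, the probability is 1 − ∫ φ(u) [Φ((c − √ρ u)/√(1 − ρ)) − Φ((−c − √ρ u)/√(1 − ρ))]^m du, evaluated numerically.

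Under Holm, the first step tests the smallest p-value at 0.05/5 = 0.01. With no true effects, a false claim occurs only if that step is passed, so for independent tests the rate is 1 − 0.99^5 = 0.049.

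| Tests (m) | ρ = 0 | ρ = 0.5 | ρ = 0.7 |
|---|---|---|---|
| 4, each at 0.05 | 18.5% | 15.6% | 13.0% |
| 5, each at 0.05 | 22.6% | 18.3% | 14.8% |
| 10, each at 0.05 | 40.1% | 28.7% | 21.3% |
| 5, Holm | 4.9% | 4.2% | 3.5% |

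The rows for 4 and 10 are there because the documents do not give the number of outcomes. Every unadjusted figure is well above the 5% of a single test.

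**Baseline adjustment.** Baseline-adjusted and unadjusted change differ by (1 − slope) × baseline gap, where slope is the regression of the final value on the baseline value. With an assumed gap of 0.2 SD and slope of 0.8, the difference is 0.2 × 0.2 = 0.04 SD. With a gap of 0.5 SD and slope of 0.7, it is 0.3 × 0.5 = 0.15 SD. In a non-randomised comparison the choice therefore affects the estimate, and it should not depend on whether a baseline t test happens to be significant.

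**The case against.** The strongest reply is that the plan makes a statement about each outcome separately, each at 5%, and nowhere says that one significant marker amounts to an effect on MetS. That stands. A reader might infer from the illustration that the plan has a false-positive rate of about 23% for its main conclusion. The documents do not support that, because the figure needs a reading rule they do not contain. What they lack is any rule in its place.

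A second reply is that MetS is less absent than it looks. It is described as a cluster of factors, the second aim refers to its markers, and the clinical-responder rule concerns a move from altered to healthy. Marker-level change is a fair reading of attenuation, and the responder analysis is plausibly related to MetS. This narrows the point without removing it, since the level of that analysis, its between-group test and any measure of prevention remain unstated.

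Third, the trial may be small and exploratory, and these are brief documents. But the plan does not call itself exploratory, and it sets a threshold for declaring a training effect. The brevity does limit the claim: a reader might infer that no primary outcome exists anywhere, whereas what can be said is that none is named here.

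Finally, a training-versus-control contrast presumes a control arm, and only the Design line suggests one. That stands, and it is why the group definition has to be settled first. The opposite inference, that there is no control group, is equally unsupported.

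**Conclusion.** The concern holds in this form: the SAP declares effects outcome by outcome at p<0.05, and in these documents there is no named primary outcome, no error control across outcomes and no stated syndrome-level analysis of MetS. The main objective therefore has no pre-specified test. That conclusion rests on the text alone and does not depend on the number of outcomes.

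The size is conditional. With five components and any single significant result read as a MetS effect, the false-positive chance is about 15% to 23% over correlations from 0.7 down to 0, against 5% for one test. These figures assume equal correlation and no true effect, and they exclude bias from non-random allocation. It would be wrong to say that the plan has no multiplicity adjustment at all, because Bonferroni is planned among groups. The change should be made before data are seen. Confidence is medium, because the outcome list and the meaning of group are not given.

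**What to change.** Before any data are seen:

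1. State what the group factor means and confirm whether an untrained control group exists. If it does, make resistance training versus control the primary contrast. If it does not, state that the design cannot attribute change to training.
2. Name one primary syndrome-level MetS endpoint at 20 weeks under a fixed published definition, tested at two-sided 0.05. The number of criteria met or a continuous severity score would each serve; the choice is the sponsor's.
3. Test the five components as secondary outcomes with Holm. State that a single significant component does not establish an effect on MetS. Report all other outcomes as estimates with the 95% confidence intervals already planned.
4. Report new MetS and resolved MetS by group, split by MetS status at baseline, so that prevention and attenuation are both visible.
5. Adjust the primary analysis for the baseline value of the endpoint whatever the baseline t test shows. Give unadjusted change as a sensitivity analysis, because the groups are not randomised.

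This needs no extra patients, but it is more than a change of wording. The MetS definition must be written down, with a measure and threshold for each component and a rule for patients treated for a component. It must also be confirmed that all five components are measured before and after, since the documents list no measurements. Fewer markers will be called significant, and an effect confined to one component would show only in the secondary tests.
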